10.5 POOLING

Data pooling incorporates two factors: combination of data across trial sites and the actual method of obtaining an estimate of the endpoint from combined data. Data will be combined from multiple trial sites for the trial analyses. The justification for this pooling is made on a clinical basis with three critical factors: The basis for pooling comes from: 1) The trial sites must implement one common protocol; 2) The sponsor must provide very close monitoring of study site compliance; and, 3) the trial sites must use common data collection procedures.¹⁶

In order to determine if there is a similar response across the sites to allow the responses to be pooled in the trial the primary safety and effectiveness proportions will be tested for homogeneity by logistic regression using a univariate model of study site within the test group. If the P-value for study site is less than 0.15, differences in study site proportions in response will be assumed to exist and the overall estimate of the proportion in the test patients will be obtained by taking a weighted average of the proportions at each site with the weight being the inverse of the variance of the proportion at that

¹⁶Meinert C. Clinical Trials: Design, Conduct, and Analysis. 1986; Oxford University Press. New York, NY

site.¹⁷ The sum of these weighted proportions divided by the sum of the weights will be the overall estimate for the study. For the safety variable, the differences of the weighted proportions will form the basis of the statistical test and for the effectiveness variable, the overall weighted proportions will be the basis of the test. The test of significance in these circumstances are fully described below.

If the heterogeneity P-value is greater than 0.15, an analysis of the primary effectiveness endpoint by the Fleiss (1993) method will be done.

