If there is heterogeneity among the study sites the test will be additionally adjusted for site differences by the method of Fleiss (1993). If the data from the study sites cannot be pooled to form a common estimate of the treatment effect, the following analysis from Fleiss (1993) will be done. Within each stratum i and treatment group j , the mean proportions across study sites is given by the following formula:

$$\bar{p}_{ij} = \frac{\sum_k W_{ijk} p_{ijk}}{\sum_k W_{ijk}}$$

Where p_{ijk} is the estimated MAE proportion from stratum i and site k for treatment j , and $W_{ijk} = 1/((1/n_{ijk})p_{ijk}(1-p_{ijk}))$. for $i=1-5$, $j = T$ for test and C for Control and k is the site number. The

²¹Mehrotra D. and Railkar R. Minimum risk weights for comparing treatments in stratified binomial trials. *Statistics in Medicine* 2000;19:811-25

differences of the weighted proportions will be computed within each propensity stratum and the test will be done using the method of Mehrota and Railkar using the minimum risk weighting factor. The formula for z is the same as above except that the within stratum estimates of the difference are the given by the following,

$$\delta_k = \bar{p}_{tk} - \bar{p}_{ck}$$

Where \bar{p}_{ik} is given by the formula above. The variance within the stratum of the difference is given by the following.

$$V_i = \left(\sum_{k=1}^{m_t} W_{itk} \right)^{-1} + \left(\sum_{k=1}^{m_c} W_{ick} \right)^{-1}$$

Where m_t is the number of sites in the treated sample and m_c is the number of sites in the control sample.

If the P-value from either test above is less than a one-sided 0.025, then the null hypothesis for this analysis will be rejected in favor of the alternative indicating that the new patients have a statistically significantly smaller rate of MAE than the historical surgical control group.

A descriptive analysis and a Kaplan-Meier analysis of the MAE composite at 30 days will be presented. The descriptive analysis will present the rates for the composite MAE and each individual adverse event that is part of the composite with corresponding 95% exact confidence intervals.

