To determine those factors that may be associated with MAE, a supportive covariate analyses will be performed by logistic regression to determine if there are differences in the rates among groups when adjusted for other factors. Covariates for these analyses will be age, gender, ASA class, cardiac/coronary artery disease (a composite variable to include arrhythmia, CHF, prior MI, CABG/PCI, heart valve repair/replacement), histories of cancer, cerebrovascular disease, coagulopathy, COPD, diabetes, hypertension, liver disease, peripheral arterial occlusive disease, renal failure, smoking, selected aneurysm characteristics, propensity class (numerical classification of the stratum based on patient's propensity score), plus any variables found to be out of balance in the comparability analyses. Because there is no exact congruence of study sites between the test and control groups it is not possible to account for study site in this analysis. To observe the effect of study site, a multivariable analysis will be done only in the test patients to determine if the study site remains a significant influence to the rate of MAE when other covariates are included in the analysis. Often the differences in study site responses are the result of differences in baseline characteristics the patients at that site such that when a model includes both the study site effect and the covariates effect, the study site no longer retains statistical significance.

If it is not possible to break the data into classes that provide adequate coverage of both treatment groups in each stratum, an alternative primary safety test will be done against a performance goal of 56% derived from the Society for Vascular Surgery (SVS) major adverse

events outcomes for infrarenal open surgical control patients.²² This is reasonably conservative as a performance goal. To this point, a recent publication finds that the rates of these major adverse events are similar between open infrarenal aneurysm repair and open complex aneurysm repair (juxtarenal, pararenal, suprarenal), with the exception of bleeding and renal events, which were significantly higher with open complex aneurysm repair.²³

The null and alternative hypotheses are provided below.

$$H_0: P_t \geq 0.56$$

versus

$$H_1: P_t < 0.56$$

where P_t is the MAE rate at 30 days in the test group

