If there is not heterogeneity in the study site MAE rates for the test patients, the univariate test will be done with the exact binomial distribution to determine if the frequency of MAE in the test group is statistically significantly less than 0.56. The formula for this test is provided below.

$$P(X \leq x_t | 0.56) = \sum_{k=1}^{x_t} \binom{n_t}{k} 0.56^k 0.44^{n_t-k} < 0.025$$

Where x_t is the number of test group patients experiencing an MAE and n_t is the number of patients in the test group. If the above expression holds for the observed x_t , the null hypothesis will be rejected and the alternative hypothesis will be accepted.

If there is heterogeneity among the study sites in MAE response, the analysis will be done by the method of Fleiss (1993). The test statistic will be given by the following formula.

$$z = \frac{(\bar{p}_T - 0.56)}{SE(\bar{p}_T)}$$

Where the formula for the weighted estimate of the proportion is given by the following formula.

²²Turnbull I, Criado FJ, Sanchez L, et al. Five year results for the Talent enhanced low profile system abdominal stent graft pivotal trial including early and long term safety and efficacy. J Vasc Surg 2010; 51:537-44.

²³Jeyabalan G, Park T, Rhee RY, et al. Comparison of modern open infrarenal and pararenal abdominal aortic aneurysm repair on early outcomes and renal dysfunction at one year. J Vasc Surg 2011;54:654-9.

$$\bar{p}_T = \frac{\sum_k W_k p_{Tk}}{\sum_k W_k}$$

And the formula for the weight in site k is given by the following

$$W_k = \frac{1}{n_k} p_k (1 - p_k)$$

And the formula for the standard error is given by the following.

$$SE(\bar{p}_T) = \left(\sum_{k=1}^{m_T} W_{Tk} \right)^{-1/2}$$

If the z has a P-value less than a one-sided alpha of 0.025, the null will be rejected and the alternative will be accepted.

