10.7 PRIMARY EFFECTIVENESS ANALYSIS

10.7.1 Primary Effectiveness Hypothesis

The primary effectiveness research hypothesis is that the treatment success rate at one year exceeds a performance goal of 80%. The null and alternative hypothesis is presented below.

$$H_0: P \leq 0.80 \quad \text{vs.} \quad H_a: P > 0.80$$

Where P is the rate of Treatment Success as defined in §10.7.2.

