10.7.3 Analysis Plan

The primary effectiveness analysis will compare the Treatment Success rate as defined previously to a target rate of 80%. The null and alternative hypotheses are defined below.

$$H_0: P_t \leq 0.80$$

$$H_1: P_t > 0.80$$

Where P_t = the proportion of treated patients who meet the Treatment Success definition. The observed proportion of patients with Treatment Success at one year post-procedure will be tested with the exact binomial distribution under the null hypothesis given in the inequality above. The formula for this expression is presented below.

$$P(X > x_t | 0.80) = \sum_{k=x_t}^{n_t} \binom{n_t}{k} 0.80^k 0.20^{n_t-k} < 0.05$$

Where x_t is the number of successes at one year and n_t is the number evaluated. If the one-sided P-value is less than 0.05, the null hypothesis will be rejected and the study hypothesis will be demonstrated.

If the study site success proportions across study site are not homogeneous, then the method of Fleiss described above will be used in the Test arm only to obtain a weighted estimate of the proportion successful. The mean proportion is found the same way as the first equation above. The test statistic becomes a z-statistic with the following formula:

$$z = \frac{(\bar{p}_T - 0.80)}{SE(\bar{p}_T)}$$

Where the formula for the weighted estimate of the proportion is given by the following formula.

$$\bar{p}_T = \frac{\sum_k W_k p_{Tk}}{\sum_k W_k}$$

And the formula for the weight in site k is given by the following

$$W_k = \frac{1}{n_k} p_k (1 - p_k)$$

And the formula for the standard error is given by the following.

$$SE(\bar{p}_T) = \left(\sum_{k=1}^{m_T} W_{Tk} \right)^{-1/2}$$

If the $z < 1.645$ ($P=0.05$, one-sided), then the null hypothesis will be rejected in favor of the alternative and the primary effectiveness endpoint will be achieved.

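### For heterogeneous sites, the 80% effectiveness test and the fallback 56% safety test print the variance as the site weight where section 10.5 requires its inverse, so neither z-statistic can reach its critical value

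*Combined protocol and SAP*

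**What the plan says.** **Trigger and weight in words.** Section 10.5 tests the site effect by logistic regression. "If the P-value for study site is less than 0.15, differences in study site proportions in response will be assumed to exist". In that case the site results are combined as "a weighted average of the proportions at each site with the weight being the inverse of the variance of the proportion". It points forward to a full description of the tests. Its closing sentence, however, assigns the Fleiss method for effectiveness to a heterogeneity P-value greater than 0.15.

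**Three worked formulas follow.**

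- Section 10.6.4, stratified comparison with the surgical control: the weight is printed inline as the reciprocal of `(1/n)p(1-p)`, which agrees with 10.5.
- Section 10.6.4, performance-goal test: if the propensity strata cannot be formed adequately, "an alternative primary safety test will be done against a performance goal of 56" per cent. For heterogeneous sites the weight is displayed as `(1/n_k)p_k(1-p_k)`. The decision rule is "If the z has a P-value less than a one-sided alpha of 0.025, the null will be rejected".
- Section 10.7.3, effectiveness: section 10.7.1 states the hypothesis that "the treatment success rate at one year exceeds a performance goal of 80" per cent. For heterogeneous sites the weight is again displayed as `(1/n_k)p_k(1-p_k)`, and the null is rejected if `z < 1.645`.

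Both performance-goal tests use `SE = (sum of W)^(-1/2)`.

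**The concern.** `(1/n_k)p_k(1-p_k)` is the estimated variance of a site proportion, not its inverse. With inverse-variance weights, the variance of the weighted mean is one over the sum of the weights, so the printed standard error is right. With variance weights the same expression has no such meaning. Sites with the least precise estimates get the most weight, sites at 0% or 100% get none, and the quantity called a standard error can be several times the whole 0-to-1 range.

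These are primary decision rules. In the heterogeneous branch the z-test replaces the exact binomial test for effectiveness, and for the 56% safety goal when that goal is in use. A rule whose outcome cannot depend on the data decides nothing. Choosing the intended formula after seeing the data is what pre-specification is meant to prevent.

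**Working it through.** **Inputs.** 97 Trial Phase patients and at most 25 sites (5.1); no site above 20% of Trial Phase enrollment (4.3), so at most 19 patients (0.20 x 97 = 19.4); goals 0.80 (10.7.1) and 0.56 (10.6.4); one-sided alpha 0.05 and 0.025.

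**The plan's own figure.** Section 10.7.2 states 80.58% power with 82 patients. The exact binomial calculation rejects at 72 or more successes, with alpha 0.0458 and power 0.8057 at 90% success. 82/0.85 = 96.5, rounded up to 97. The stated figures are reproduced; they belong to the exact test and do not involve the weights. The plan gives no numerical result for the weighted tests.

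**Simple bound with the printed weight.** `p(1-p)/n` is 0 for a one-patient site and largest at n = 2, p = 0.5: 0.25/2 = 0.125. With 25 sites:

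- sum of W <= 25 x 0.125 = 3.125, so SE >= 3.125^(-1/2) = 0.566
- effectiveness z <= (1 - 0.80)/0.566 = 0.35, against 1.645
- safety z >= (0 - 0.56)/0.566 = -0.99, against -1.96

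**Sharper bound.** Since `z = (pbar - c) x sqrt(sum W)`, the Cauchy-Schwarz inequality gives `z^2 <= sum of W_k(p_k - c)^2`. Maximising this over every allocation of 97 patients to at most 25 sites of at most 19 gives:

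- effectiveness z at most 0.031 (0.028 with 82 patients). Nine sites at 8/9 and two at 7/8 reach 0.0305.
- safety z no lower than -0.33. Twenty-two sites at 1/4 and three at 1/3 give sum W = 1.253, pbar = 0.265, SE = 0.893, z = -0.331.

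Combining small sites under 10.4 cannot escape these limits, because it reduces the number of sites and the combined site may not exceed the largest one.

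**Illustrations.** The site splits are assumed. All three have a likelihood-ratio site P-value below 0.15. Site sizes are 19, 19, 19, 19, 11 and 10.

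| Data (events by site) | Site P | Weight | pbar | SE | z |
|---|---|---|---|---|---|
| Success 86/97 (18, 18, 18, 13, 10, 9) | 0.146 | printed | 0.844 | 5.29 | 0.008 |
| same | | inverse variance | 0.925 | 0.026 | 4.79 |
| MAE 16/97 (2, 6, 2, 1, 4, 1) | 0.116 | printed | 0.247 | 4.31 | -0.073 |
| same | | inverse variance | 0.115 | 0.031 | -14.3 |
| Success 58/97 (7, 16, 8, 13, 6, 8) | 0.013 | printed | 0.594 | 3.49 | -0.059 |
| same | | inverse variance | 0.639 | 0.045 | -3.60 |

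For the first row the printed weights are 0.00262 (three sites), 0.01137, 0.00751 and 0.00900. They sum to 0.03576, so SE = 0.03576^(-1/2) = 5.29 and z = (0.844 - 0.80)/5.29 = 0.008.

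The 58/97 data set (60% success) gives z = -0.059, which satisfies the printed `z < 1.645` and would count as success.

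**Limit of the simple correction.** `n_k/[p_k(1-p_k)]` is undefined at a site with 0% or 100%. At 90% success the chance of that is 0.9^10 + 0.1^10 = 35% for a site of 10 and 0.9^19 + 0.1^19 = 14% for a site of 19. In a simulation of 97 patients with a common 90% success rate and assumed site sizes, 98% (6 sites) to 100% (10, 16 and 25 sites) of the data sets with site P < 0.15 contained at least one such site.

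**The case against.** **It may be a conversion fault.** The displayed equations in 10.6.4 are visibly damaged elsewhere: one denominator repeats the same subscript. The one correct weight is inline text, while the two faulty ones are displays, where an outer reciprocal is easily lost. One source equation used twice would repeat the fault. This stands as a reason to check the source page first. It is not shown to be the explanation.

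**The intended method is clear.** The words of 10.5, the inline weight in 10.6.4 and the standard error all point to inverse variance, and a statistician who met a standard error of 5 would notice. That is fair about intent. The printed rule still contradicts its own definition in a primary test, and the two versions give opposite answers.

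**Stronger readings that the documents do not support.**

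- A reader might infer that the device could never succeed on effectiveness in this branch. Under the printed sign it would always pass; it could never pass only if the sign alone were corrected.
- A reader might infer that all the safety testing is affected. The main comparison with the surgical control prints the correct weight. The 56% test needs two contingencies: failure of the propensity adjustment and heterogeneous sites.
- A reader might take 15% as the chance of entering the branch when sites do not differ. That is only the nominal level. In the same simulation the rate ran from about 23% (6 sites) to 6% (25 sites).

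**Conclusion.** The contradiction is real and affects a primary decision rule. With the printed weight, the safety performance-goal test cannot reject for any data. The effectiveness test always rejects as printed, whenever z is defined, and never rejects if only the inequality is reversed. The bounds of about 0.03 and -0.33 are algebraic. They rest only on 97 patients, at most 25 sites and at most 19 patients per site. The illustrative z values rest on assumed site splits, and the simulated rates on assumed site sizes and 90% success.

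The scope is the heterogeneous-site branch only. The trigger for that branch is itself stated in two incompatible ways in 10.5. The exact binomial tests for homogeneous sites and the sample size are not touched. Whether the fault is in the source or in its conversion remains open until the original page is read.

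**What to change.** 1. Check the original pages of 10.6.4 and 10.7.3 for a lost reciprocal.
2. In both places print `W_k = n_k/[p_k(1-p_k)]` and keep `SE = (sum of W)^(-1/2)`.
3. In the same edit, state a rule for sites at 0% or 100%. Either specify a continuity adjustment to p_k inside the weight, or use site-size weights `n_k/N` with the standard error re-derived as `sqrt(sum of (n_k/N)^2 x p_k(1-p_k)/n_k)`. The choice matters and must be made in advance. On the 86/97 illustration, site-size weights give pbar = 0.887, SE = sqrt(8.757/97^2) = 0.0305 and z = 2.84, against 0.925 and 4.79 with inverse-variance weights.
4. Correct the effectiveness rule to `z > 1.645`. The weight and the sign must be corrected together.
5. Reconcile the closing sentence of 10.5 (P greater than 0.15) with the P < 0.15 trigger.

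The cost is one formula corrected in two places, one added rule and two corrected sentences. No new data, patients or sample-size calculation are needed. The zero-variance rule is the only part that needs a decision rather than a correction.

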[¥]The baseline high resolution, contrast-enhanced CT scan (2mm or less slice spacing) performed within three months prior to enrollment will be reviewed by the independent core lab for patient eligibility determination. Evaluations of endograft performance, renal stent graft patency and integrity, and stent graft patency and integrity will be made based upon post-operative CT scan evaluations by the core laboratory.

*Follow-up windows are ±2 weeks (1 month visit); ±1 month (6 month visit); ±2 months (Year 1 visit); ±3 months (Years 2 through 5 visits)

Statistical

Considerations: *Study Population:* The intent to treat (ITT) population in this study consists of all patients who are enrolled and treated.

Trial Success, Safety: The primary safety analysis is **Major Adverse Events (MAE)**, as previously defined. This analysis is limited to patients enrolled in the Trial Phase (i.e., roll-in patients are not included and will be reported as a separate feasibility group). The primary endpoint is to show that the % of patients with an MAE is statistically superior to that in the Endologix open surgical historical control group at 30 days. The hypothesis test will be evaluated by the exact test as a one-tailed test, using significance level $\alpha=0.025$. Multivariable analyses will be used to assess predictors of trial success.

Trial Success, Effectiveness: The primary effectiveness analysis is **Treatment Success**, as previously defined. This analysis is limited to patients enrolled in the Trial Phase (i.e., roll-in patients are not included and will be reported as a separate feasibility group). The primary endpoint is to show that the % of patients with Treatment Success is statistically superior to the target rate of 80% at one year. The hypothesis test will be evaluated using the exact binomial distribution as a one-tailed test, using significance level $\alpha=0.05$. Multivariable analyses will be used to assess predictors of trial success.

Additional Evaluations: Appropriate statistical methodology will be used to analyze all additional evaluations.

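### Section 10.5 assigns the Fleiss method to the primary effectiveness endpoint when sites are homogeneous, in conflict with Section 10.7.3, the synopsis and the sample size, which use the exact binomial test

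*Combined protocol and SAP*

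**What the plan says.** Section 10.5 (Pooling) tests site homogeneity by logistic regression and states the heterogeneous case first: "If the P-value for study site is less than 0.15, differences in study site proportions in response will be assumed to exist". The site proportions are then combined with inverse-variance weights, citing Fleiss, and "for the effectiveness variable, the overall weighted proportions will be the basis of the test". The section's closing sentence covers the other side of the threshold: "If the heterogeneity P-value is greater than 0.15, an analysis of the primary effectiveness endpoint by the Fleiss (1993) method will be done". Section 10.5 does not mention the exact binomial test.

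Four other places bear on the same choice:

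- Section 10.7.3 (effectiveness analysis plan): "The observed proportion of patients with Treatment Success at one year post-procedure will be tested with the exact binomial distribution". The exception follows: "If the study site success proportions across study site are not homogeneous, then the method of Fleiss described above will be used".
- Synopsis, effectiveness paragraph: "The hypothesis test will be evaluated using the exact binomial distribution as a one-tailed test, using significance level" 0.05.
- Section 10.7.2 (sample size): computed from the exact binomial distribution, with 82 patients, 80.58% power, a true rate of 90% and one-sided alpha 0.05. The hypothesis in 10.7.1 is that "the treatment success rate at one year exceeds a performance goal of 80"%.
- Section 10.6.4 (safety performance goal): "If there is not heterogeneity in the study site MAE rates for the test patients, the univariate test will be done with the exact binomial" test, with Fleiss used if there is heterogeneity.

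**The concern.** When the site P-value exceeds 0.15, Section 10.5 calls for Fleiss and Section 10.7.3 calls for the exact binomial test. Section 10.7.3 gives no threshold for homogeneity, so the reader has to go back to 10.5 for it, and there finds the conflicting instruction.

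This is the case the design expects. If sites truly do not differ and the homogeneity test holds its nominal level, about 1 − 0.15 = 85% of trials fall on the P > 0.15 side. Alpha and power were worked out only for the exact test. If the conflict is still open when the data are seen, the choice between two tests with very different error rates is made after the fact, and it could decide the effectiveness result.

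**Working it through.** **1. Both sides of the threshold**

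| Site P-value | Section 10.5 | Section 10.7.3 |
|---|---|---|
| Below 0.15 (heterogeneous) | Inverse-variance weighted proportion (Fleiss) | Fleiss z-test |
| Above 0.15 (homogeneous) | Fleiss | Exact binomial |
| Exactly 0.15 | Not assigned | No threshold given |

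The sections agree in the first row and conflict in the second.

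**2. The plan's own figure (10.7.2)**

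Inputs: n = 82, null rate 0.80, alternative 0.90, one-sided alpha 0.05. Find the smallest r with P(X ≥ r | 82, 0.80) < 0.05.

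- r = 71: tail probability 0.0836, too large.
- r = 72: tail probability 0.0458, so reject at 72 or more of 82.
- Power: P(X ≥ 72 | 82, 0.90) = 80.57%, against 80.58% stated.
- Enrolment: 82/0.85 = 96.5, rounded up to 97.

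The stated figures reproduce as those of the exact test. If all 97 patients are analysed after imputation, the exact test rejects at 85 or more, with alpha 0.0346 and power 83.0%.

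**3. What the weighted test does with homogeneous sites**

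The documents give no site sizes. Assumption: 82 patients in 5, 10 or 20 near-equal sites with a common success rate, 100,000 simulated trials per scenario, rejecting when z = (weighted proportion − 0.80)/SE exceeds 1.645. The weight is n/[p(1 − p)], which is undefined at a site with 0% or 100% success. The plan does not say how such sites are handled, so two conventions were tried.

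| Sites | Drop such sites: type I error | Drop such sites: power at 0.90 | Add 0.5 to counts in the variance: type I error |
|---|---|---|---|
| 5 | 22% | 85% | 25% |
| 10 | 0.25% | 5.5% | 51% |
| 20 | 0% | 0% | 58% |

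The zeros can be checked by hand. Once no-failure sites are dropped, a four-patient site can show at most 3/4 = 0.75 and a five-patient site at most 4/5 = 0.80, so the weighted mean cannot exceed the goal. The simulation applied the test to every homogeneous data set rather than only to those with site P above 0.15, so the figures indicate scale and are not exact branch-specific rates.

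**4. Separate point: sites with no usable weight**

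With 97 patients in k equal sites at 90% success, the chance of at least one site without a failure is 1 − (1 − 0.9^m)^k, where m is the site size.

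- k = 5, m = 19.4: 0.9^19.4 = 0.130; 1 − 0.870^5 ≈ 50%.
- k = 10, m = 9.7: 0.9^9.7 = 0.360; 1 − 0.640^10 ≈ 99%.
- k = 24, m = 4: 0.9^4 = 0.656; 1 − 0.344^24 > 99.99%.

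Five sites is about the fewest that the 20% cap per site in Section 4.3 allows (strictly, 5 × 19 = 95 falls just short of 97). The maximum is 25.

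**The case against.** The strongest reply is that the plan does have a primary effectiveness test. The synopsis, 10.7.2 and 10.7.3 all name the exact binomial test, and 10.6.4 has the same structure for safety. Section 10.5 itself refers forward to later text for the significance tests in the heterogeneous case. Its last sentence says only that an analysis by Fleiss will be done, not that it replaces the exact test. The word *greater* may be a slip for *less*, or an additional analysis may be meant.

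Most of this stands. A reader of 10.5 might infer that the exact test would never be primary, or that the primary test is undetermined. Neither holds for the document as a whole; both come from reading 10.5 alone. What remains is that the sentence concerns the primary endpoint, directly follows the rule for the primary test and is not labelled supportive. The text does not settle whether it is a slip or an extra analysis.

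A reader might also infer that the weighted method is virtually certain to fail at the expected site sizes. The documents give no expected sizes: 25 sites is a maximum, and the chance in step 4 runs from about 50% upward. Section 10.4 allows sites with four or fewer patients to be combined, although it is written for baseline comparability and is not extended to the Fleiss test. As printed in 10.7.3, the weight is p(1 − p)/n rather than its reciprocal, so a no-failure site would get weight zero instead of an undefined one. In any case, this weakness belongs to the weighted method wherever it is used. It does not measure the conflict between the sections.

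**Conclusion.** The conflict is real and confined to one sentence. When sites are homogeneous, 10.5 assigns Fleiss to the primary effectiveness endpoint, while 10.7.3, the synopsis and the sample size rest on the exact binomial test. The intended rule can be inferred with reasonable confidence, but a pre-specified primary test should not depend on inference.

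The 80.58% power and the 0.05 alpha belong to the exact test only. Taking 10.5 literally gives a test whose type I error, under the assumed site sizes and with unusable sites dropped, ranges from 0% to about 22% against a nominal 5%. Those values depend on near-equal sites, on the number of sites and on how zero-variance sites are handled, none of which the plan fixes for this test. The conflict between the sections depends on none of these assumptions.

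**What to change.** Replace the last sentence of Section 10.5 with: *When the site P-value is 0.15 or greater, the primary effectiveness endpoint is tested with the exact binomial test of Section 10.7.3; any Fleiss estimate in that case is supportive.* This aligns 10.5 with 10.7.3, 10.7.2, the synopsis and the rule in 10.6.4, and it settles the case of P exactly 0.15.

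The cost is one sentence, to be changed before the effectiveness data are analysed. The sample size stays at 97, and no other calculation changes.

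The fix does not deal with no-failure sites when P is below 0.15. For that branch the plan separately needs a stated rule for sites with 0% or 100% success and one consistent weight formula across 10.5, 10.6.4 and 10.7.3.
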